Ventricular tachycardia (VT) is an important cause of morbidity and mortality in almost all forms of heart disease[1, 2]. Most of the patients with structural heart disease will have implantable cardioverter defibrillators (ICDs), which reduce the risk of sudden cardiac death[3]. Although ICDs are effective in terminating VT and preventing sudden cardiac death, shocks from ICDs reduce quality of life, and multiple shocks are associated with post-traumatic stress disorder[4, 5]. Most importantly, ventricular arrhythmia episodes and ICD shocks are also associated with increased overall-mortality and progression of heart failure, although the extent to which arrhythmia recurrences actually contribute to adverse outcomes or are simply markers for deteriorating cardiac status remains unclear[6]. Anti-arrhythmic drugs (AADs) are usually the first line therapy for VT. Of all AAD classes, the most commonly used for long-term prevention of VT recurrence are the Vaughan Williams class III AADs (sotalol, amiodarone and dofetilide). Unfortunately, AADs are often insufficient in suppressing VT and they carry a significant adverse effect profile. In cases of recurrent VT, catheter ablation (CA) has been shown to be a safe and effective treatment modality [7]. However, patients with structural heart disease who undergo CA still have substrate that predisposes them to VT recurrences. In addition, catheter ablation lesions heal and evolve over days to weeks, resulting in VT recurrences that are particularly associated with poor outcomes[8-10].

Although most patients undergoing VT ablation are on AADs, it is currently unknown the best management strategy of AADs following VT ablation, i.e., it is unclear if these patients should continue AADs or not.

2. Rationale and Specific Aims

Catheter ablation is a valuable option to control recurrent VT in patients with structural heart disease [3, 7]. However, after VT ablation the VT substrate remains and ablation lesions heal and evolve over days to weeks, such that some patients will suffer recurrent VT that is associated with worse mortality than patients who remain free of VT. Currently, it is not known if continuation of AADs following VT ablation can prevent these recurrent VT episodes. Of the currently available AADs, class III have the strongest antiarrhythmic profile, however, their significant adverse effect profile limits their use. Therefore, there is equipoise in clinical practice that benefits of class III AADs preventing recurrent VT outweighs the risks of their toxicities.

The specific aim of this pilot study is to obtain preliminary data to evaluate whether the strategy of continuation of class III AADs following CA for VT, improves VT-free survival and reduces readmissions. The goal of this study will be to answer the following question:

Among patients with structural heart disease who undergo VT ablation, does continuation of class III AADs 3 months after ablation, increases VT-free survival compared to discontinuation of antiarrhythmic drug therapy?

3. Hypothesis

We hypothesize that VT-free survival after catheter ablation is greater with continuation of class III AADs.

4. Inclusion/Exclusion Criteria

1. Age >18 years.
2. Able to give written, informed consent
3. Structural heart disease.
4. Implanted and normally functioning ICD or undergoing ICD implant at index admission.
5. Undergoing radiofrequency ablation procedure for sustained monomorphic VT.
6. Primarily on class III AADs for VT.
7. No clinically relevant VT inducible at the end of VT ablation
8. No clinically relevant VT inducible on non-invasive programmed stimulation following VT ablation.

Exclusion Criteria:

1. LV assist device in place
2. Decompensated heart failure and/or requiring continuous inotropic therapy and/or awaiting cardiac transplantation
3. Ongoing acute coronary syndrome.
4. Mechanical prosthetic aortic and mitral valves.
5. Pedunculated or mobile left ventricular thrombus.
6. Persistency of clinically relevant VT at the end of catheter ablation.
7. Absolute contraindications for amiodarone.
8. Participation in other trial.
9. Clinical VT induced on NIPS after VT ablation.
10. Another reason for continuation of class III AADs (i.e., atrial fibrillation).

5. Enrollment/Randomization

A patient will be identified as a candidate for participation in this study while receiving care at Vanderbilt University Medical Center. The clinical team will contact the patient in-person while being evaluated for VT ablation. The clinical team will ask the patient if they are interested to discuss participation in the clinical trial. If yes, information about participation will be provided by approved research staff. The patient may sign the consent document, decline, or defer until the day prior to ablation. At that time, research staff will again be available to

provide further information and/or obtain consent. Patients who decline participation will continue to receive usual care and the decision to not participate will not interfere with their medical care. Each candidate will receive a copy of the signed consent form. The consent form is presented in Appendix 1.

Patients will have VT ablation. Those with no evidence of clinical VT inducibility after ablation will then undergo Non-Invasive Programmed Stimulation (NIPS) prior to discharge. NIPS will be performed as there is evidence that patients with inducible clinical VT on NIPS after VT ablation have greater risk of VT recurrence [11] and might not be appropriate to withhold anti-arrhythmic therapy for those with inducible VT in NIPS.

Patients that meet inclusion criteria and agree to participate will be randomized and allocated to continue class III AADs or discontinuation using block randomization, stratified by type of AADs used until goal enrollment is achieved. The randomization sequence will be created using STATA 14.2 (StataCorp, College Station, TX, USA) statistical software.

Adherence to study-assigned group will be achieved by clinician education and reminders in routine daily meetings performed by the electrophysiology service.

Before enrollment begins, approval from the Institutional Review Board of Vanderbilt University Medical Center will be obtained, and the trial will be registered in ClinicalTrials.gov.

6. Outcome measures

The primary outcome will be VT-free survival, a composite of all-cause mortality and VT recurrence one year after VT ablation. Secondary outcomes will be all-cause mortality, VT recurrence, incidence of VT storm, and readmission for heart failure for one year after VT ablation. Both self-terminating sustained VTs (>30 seconds or hemodynamic instability) and VT requiring device therapies for termination will be considered as recurrences when considering VT recurrence.

Subgroup analysis.

The primary and secondary outcomes will also be investigated according to type of cardiomyopathy (ischemic vs dilated) and according to type of AADs.

7. Study Procedures

Enrollment:

At the time of enrollment, baseline information pertaining to symptoms and details clinical presentation, imaging, and heart catheterization procedures will be obtained from examination of their medical record and recorded in a Redcap database

VT ablation procedure

Ablation will be performed according to our usual practice. When feasible, prior to ablation class III AADs will be held for 72 hours prior to ablation per usual practice in our institution.

Ablation will be standardized and performed in all participants per usual care and without any differences in protocol. Briefly, in fasting state patients are taken to the electrophysiology laboratory and are continuously monitored during the ablation with external surface EKG leads.

The procedure will be performed with the usual sterile preparation under moderate sedation or general anesthesia. The left ventricular endocardial cavity will be accessed via either retrograde aortic or trans-septal access. A hexapolar catheter will be positioned in the right ventricular apex. A mapping catheter or a multi-polar mapping catheter will be used to collect voltage and activation data from the left ventricle during sinus rhythm or RV apical pacing. Areas of slow conduction with crowding of isochrones will be outlined.

Programmed stimulation for initiation of VT will be performed at the start of the procedure after catheter are placed and use 1, 2, and then 3 extrastimuli during 2 paced cycle lengths from 2 RV sites. Systemic anticoagulation with heparin will be required for LV mapping and dosed per usual protocol. After induction of VT the specific extra-stimulus protocol (site, drive cycle length and extra-stimuli) will be recorded. A comprehensive endocardial substrate map will then be created during sinus rhythm or RV apical pacing to capture both voltage and activation to the offset of the local electrogram. Areas of interest on the basis of pace-mapping or electrogram characteristics will be tagged. If at any point during this procedure, the origin of VT is located in the epicardial surface, pericardial access will be obtained and an epicardial substrate map will be generated. After completion of the substrate map repeat programmed stimulation for initiation of VT will be performed using the same protocol as the start of the case.

Then, ablation will be performed to target all clinically relevant VTs, which will be defined as all sustained monomorphic VTs having a cycle length within 20 ms longer than the fastest VT documented prior to ablation. Ablation of VTs of shorter cycle lengths will be performed whenever feasible and clinically indicated. Anticoagulation following catheter ablation will follow usual practice.

Non-Invasive Programmed Stimulation

Patients with no evidence of clinical VT being inducible at the end of ablation and no spontaneous VT recurrence will undergo NIPS prior to hospital discharge, according to our usual practice. Patients will need to provide written informed consent on the day of or before of this procedure as done in usual practice. If the patient refuses to consent will be excluded from the study.

Briefly, under fasting condition, patients will undergo NIPS via the right ventricle ICD per usual protocol, which is the protocol used as usual practice in our division when NIPS is performed, under monitored anesthesia care (MAC) and continuous external surface EKG lead monitoring.

Response to these stimuli will be categorized as “inducible clinical VT” and “No clinical VT inducible”. Patients with inducible clinical VT will be excluded of our study.

ICD programming guidelines:

After catheter ablation, patient's ICD programming to detect and treat VT will be adjusted as per usual practice in our division based on published guidelines[7]. VT detection will be programmed depending on clinical VT rate.

- **If VT is 200 bpm or faster**, detection will be set at 165-171 bpm but without therapy programmed unless HR is > 200 bpm.
- **If VT is slower than 200 bpm**, detection programmed at 20 bpm slower than the known VT cycle length.
- **If the known VT is 140-150 bpm**, set detection at 130 bpm.
- **If the known VT is slower than 140 bpm**, detection should be programmed 10 bpm slower than the known VT.

In addition, will allow delay in therapy of 6-12 seconds. Anti-tachycardia pacing is recommended in all zones.

Follow-up

Patients will be evaluated per usual care after VT ablation by their treating electrophysiologist. This is at two to four weeks after ablation, and then at three months intervals (either in clinic or via remote ICD interrogation) for one year. ICD interrogations will be performed in each visit and we will ask to receive alarms for episodes of VT/VF and therapies delivered. Changes in medical therapy and ICD settings will be at the discretion of the treating electrophysiologist. Our consent form will include request of consent to access remote as well as in-office ICD interrogations. Most of these patients will likely have been already enrolled in a VT registry maintained by the arrhythmia service and this will route us the interrogations with no need to have the patient come for specific appointments with us for this trial.

8. Risks of Investigational Agents/Devices (side effects)

The added risks of continuation of class III AADs include risk of hyperthyroidism, hypothyroidism, hepatotoxicity, pulmonary fibrosis, corneal deposits, optic neuropathy, skin deposition, tremors and increased defibrillator thresholds, polymorphic ventricular tachycardia, torsades des pointes, bradycardia, fatigue, weakness, headache, edema, depression, thrombocytopenia, angioedema, skin rash.

However, most of these patients have been already tolerating these medications over several months/years. Furthermore, we expect that in the long-term, preventing VT will result in reduction of out-of-hospital VT/VF leading to ICD shocks which are associated with reduced quality of life and increased mortality.

9. Reporting of Adverse Events or Unanticipated Problems involving Risk to Participants or Others

Any unanticipated adverse events will be reported by the Principal Investigator according to applicable IRB policy. The PI is fully engaged in the performance of the study and this ensures that adverse events would be readily known by the PI and reported in a timely manner.

10. Study Withdrawal/Discontinuation

If an individual decides to withdraw their consent by informing study staff in writing or verbally, we will withdraw the participant. Contact information for the PI and study staff will be made available to the participant upon enrollment in the consent document.

11. Statistical Considerations and analysis plan

No studies have previously addressed this question; therefore we have no clear expectation on possible effect size and plan to perform this trial as a pilot study aimed at including all patients possible in a time frame of 12-24 months to then inform power size calculations for a larger and blinded clinical trial. We plan to enroll 75 patients per arm.

An intention to treat analysis will be performed. Analysis for the primary outcome will be accomplished by using log-rank statistic. Cox proportional-hazards regression will be used to estimate relative risks and 95% confidence intervals and adjust for differences in baseline outcome predictors. Differences in secondary outcomes will be calculated using log-rank statistic and cox proportional-hazards regression for all-cause mortality, VT-free survival, hospital readmissions and with unpaired t test for VT storm.

Interim analysis of the primary endpoint and drug adverse events will be planned every 6 months from study initiation. An independent statistician blinded to the treatment groups will perform the analysis and report findings to the data and safety monitoring committee who will decide the continuation of the study.

12. Privacy/Confidentiality Issues

A variety of measures will be utilized to ensure participant privacy:

Data will be stored in REDCap using the participant's study ID. Their REDCap data record may contain some identifying information. Subjects will be tracked using their study ID. The identifiable data, excluding date of procedures, will reside as a separate form under the data entry sections labeled "Registration/PHI" within our REDCap database which will allow us to exclude access to the identifiable information, excluding date of procedures, if necessary. Minimal paper records will be kept, and they will be kept locked in a cabinet.

Researchers are trained in HIPAA privacy regulations and other applicable privacy policies at Vanderbilt University. No information will be released, nor will participation in the research be acknowledged, to any party except where compulsory according to law or Vanderbilt policy. There may be unknown or unanticipated adverse effects from participation in this trial for which the PI and study team will remain observant.

13. Follow-up and Record Retention

Patients will be evaluated per usual care after VT ablation by their treating electrophysiologist. This is at two to four weeks after ablation, and then at three months intervals (either in clinic or via remote ICD interrogation) for one year. ICD interrogations will be performed in each visit and we will receive remote alarms for episodes of VT/VF. Changes in medical therapy and ICD settings at follow up will be at the discretion of the treating provider.

Data will be retained indefinitely. Electronic data may be destroyed earlier at the request of the participant. If so, electronic records will be deleted from the REDCap database, paper copies will be deposited into locked containers designated for shredding of confidential patient information.

14. References

1. John, R.M. and W.G. Stevenson, *Noninvasive Ablation of Ventricular Tachycardia*. N Engl J Med, 2017. **377**(24): p. 2388-2390.
2. Al-Khatib, S.M., et al., *2017 AHA/ACC/HRS Guideline for Management of Patients With Ventricular Arrhythmias and the Prevention of Sudden Cardiac Death: Executive Summary: A Report of the American College of Cardiology/American Heart Association Task Force on Clinical Practice Guidelines and the Heart Rhythm Society*. Heart Rhythm, 2017.
3. Epstein, A.E., et al., *2012 ACCF/AHA/HRS focused update incorporated into the ACCF/AHA/HRS 2008 guidelines for device-based therapy of cardiac rhythm abnormalities: a report of the American College of Cardiology Foundation/American Heart Association Task Force on Practice Guidelines and the Heart Rhythm Society*. J Am Coll Cardiol, 2013. **61**(3): p. e6-75.

4. Schron, E.B., et al., *Quality of life in the antiarrhythmics versus implantable defibrillators trial: impact of therapy and influence of adverse symptoms and defibrillator shocks*. Circulation, 2002. **105**(5): p. 589-94.

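### VT recurrence is defined without regard to morphology, so the plan does not ensure that polymorphic VT or torsades, listed risks of continuing the drug, are identified or reported as harms

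*Combined protocol and SAP*

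**What the plan says.** The index arrhythmia is specific. Section 4 admits patients "Undergoing radiofrequency ablation procedure for sustained monomorphic VT", and Section 7 also defines the ablation targets as monomorphic.

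The outcome is not specific. Section 6 states: "The primary outcome will be VT-free survival, a composite of all-cause mortality and VT recurrence one year after VT ablation." Recurrence has two limbs. The first is VT that stops by itself but lasts more than 30 seconds or causes haemodynamic instability. For the second, "VT requiring device therapies for termination will be considered as recurrences when considering VT recurrence". Neither limb mentions morphology. The other outcomes are: "Secondary outcomes will be all-cause mortality, VT recurrence, incidence of VT storm, and readmission for heart failure for one year after VT ablation." None is a safety outcome for the drug.

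Section 8 lists the added risks of continuing class III drugs, among them "polymorphic ventricular tachycardia, torsades des pointes, bradycardia".

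Three other places bear on the point:
- Section 7, Follow-up: "ICD interrogations will be performed in each visit and we will ask to receive alarms for episodes of VT/VF and therapies delivered." No rhythm classification or adjudication step is described.
- Section 9 has the principal investigator report unanticipated adverse events under IRB policy.
- Section 11 plans an interim analysis of the primary endpoint and of drug adverse events every six months, reported to a data and safety monitoring committee. It does not define drug adverse events.

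**The concern.** Section 2 frames the clinical question as a balance: does preventing recurrent VT outweigh the toxicity of class III drugs? Polymorphic VT and torsades belong on the toxicity side, by the protocol's own list. Under the Section 6 rule, an episode that is sustained, unstable or treated by the device goes into the prevention count, where it looks the same as a return of the ablated arrhythmia.

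At stake is how the pilot can be read. If the pooled result shows little difference between arms, the listed outcomes and analyses cannot tell a drug that prevents little monomorphic VT from one that prevents some and provokes some polymorphic VT. The planned subgroup analysis by type of antiarrhythmic drug has the same limit. Section 11 says that the pilot is meant to inform a larger trial, whose designers would want to see the two effects apart.

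**Working it through.** The plan states no figure on this point, so the check is mainly a reading of the sections side by side.

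**1. Where each kind of episode goes**

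| Episode | Section 6 | Recorded as a harm? |
|---|---|---|
| Monomorphic VT, sustained, unstable or device-treated | Recurrence | Not applicable |
| Polymorphic VT/torsades, device-treated | Recurrence | Possible, not required |
| Polymorphic VT/torsades, self-terminating, over 30 s or unstable | Recurrence | Possible, not required |
| Polymorphic VT/torsades, self-terminating, untreated, shorter and stable | No outcome event | Possible, not required |

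The first three rows cannot be told apart in any listed outcome. The fourth is foreseeable, because the ICD programming guidelines in Section 7 allow a 6-12 second delay before therapy.

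**2. Routes by which such an episode could be reported as a harm**
- Section 9 covers unanticipated events. Polymorphic VT and torsades are listed risks, so they are arguably anticipated.
- The Section 11 interim review covers drug adverse events. The term is undefined, and nothing says whether an episode already counted as recurrence is also counted there.
- The Section 11 final analysis uses log-rank and Cox methods for the primary outcome, mortality, VT-free survival and readmissions, and a t test for VT storm. It describes no between-arm comparison of harms.

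One route is open (the interim review), but none is assured.

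**3. What a safety table could show with 75 patients per arm**
- With no cases, the exact two-sided 95% upper limit is 1 − 0.025^(1/75) = 0.048, or 4.8%.
- The documents give no proarrhythmia rate. For assumed one-year risks of 1%, 2% and 4% in the continuation arm, the expected numbers of patients are 75 × risk = 0.75, 1.5 and 3. The chance of at least one is 1 − (1 − risk)^75 = 53%, 78% and 95%.

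**4. How far pooling could move the hazard ratio (all rates assumed)**
- Take a control risk of 40% and a hazard ratio of 0.70 for monomorphic VT or death. The risk on drug is 1 − 0.60^0.70 = 0.301.
- Add an independent polymorphic risk t in the continuation arm only: 1 − (1 − 0.301)(1 − t) = 0.308, 0.322 and 0.336 for t = 1%, 3% and 5%.
- The pooled hazard ratio is ln(1 − risk)/ln(0.60) = 0.72, 0.76 and 0.80. At a control risk of 30% it is 0.73, 0.79 and 0.84; at 50% it is 0.71, 0.74 and 0.77.
- Events for 80% power at two-sided 5%, at 40% control risk, are 4(1.96 + 0.8416)²/ln(HR)². This gives 247 at 0.70, then 290, 415 and 633 at the unrounded pooled ratios.

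Step 4 is shown because a reader is likely to try it. It does not measure the defect, for the reason given under the objection.

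**The case against.** **The primary is a legitimate choice.** Section 2 asks about VT-free survival under a strategy of continuation. Counting every sustained or treated VT estimates the net effect of that strategy. If the drug provokes polymorphic VT, the pooling works against continuation, so it cannot flatter the hypothesised benefit. No section says that recurrence must mean return of the ablated arrhythmia. This stands, and the composite should not change.

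**Harms are not absent from the plan.** A reader might infer that proarrhythmia would never be reported as a harm, or would be reported as zero. The documents do not support that. Section 11 sends drug adverse events to the monitoring committee every six months, a torsades episode could naturally be reported there, and nothing prevents an episode from being both an endpoint and an adverse event. What remains is that nothing requires it.

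**No sample-size cost follows.** A reader might infer from step 4 that the follow-on trial would be sized on a diluted ratio. If that trial keeps the all-VT composite, the net ratio is the correct planning value, and the larger event counts would remain after the fix. The illustration is also one-sided: it puts no polymorphic VT in the discontinuation arm, and Section 8 notes that most patients have already tolerated these drugs for months or years.

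**The gap is partly generic.** Drug adverse events are undefined for thyroid, hepatic and pulmonary toxicity too. That is so, but those harms are not absorbed into the efficacy endpoint by a stated rule. Polymorphic VT and torsades are.

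**Conclusion.** The point holds as a gap in classification and reporting. The recurrence rule takes in a harm that Section 8 attributes to one arm, briefer episodes fall outside every listed outcome, and no listed outcome or final analysis separates the two. The six-monthly review might catch such episodes, but the plan does not ensure it.

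This rests on the wording of Sections 4, 6, 8, 9 and 11 and needs no assumed rate. Its numerical size cannot be stated, because the documents give no proarrhythmia rate for either arm. At an assumed 1-4% in the continuation arm, about one to three patients would be affected. This is an inexpensive improvement that lets the pilot show both sides of the balance in Section 2. It is not a flaw that invalidates the primary analysis.

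**What to change.** Keep the composite primary unchanged.

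- **Section 6, classification.** Classify each recorded VT/VF episode from its stored electrogram or ECG as monomorphic, polymorphic/torsades, VF or unclassified. Mask the assigned arm on the tracings given to whoever already reads the interrogations for the study. Section 11 describes the later trial as the blinded one, which implies that this one is open, and an unmasked reader could label episodes differently by arm.
- **Section 6, safety outcome.** Tabulate device-recorded or ECG-documented polymorphic VT/torsades by assigned arm in the final report (patients, episodes, exact 95% confidence intervals). State that these episodes are also included in the drug adverse events sent to the six-monthly review, whether or not they count as recurrence.
- **Section 11, secondary estimate.** Add a cause-specific Cox estimate for monomorphic VT recurrence, with death as a competing event and patients kept at risk after a polymorphic episode. Report it beside the all-VT result and do not let it replace that result.

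The cost is one REDCap field per episode, the masking of tracings already received, one table and one model. Enrolment, treatment and ICD programming do not change. There are limits: counts will be small, some episodes will have no usable tracing and must be shown as unclassified, and runs below device detection will be missed. Classification is best done as episodes arrive, since electrograms may not be available later.

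### For short stable VT and VT near the detection rate, ICD settings decide whether an episode counts as a recurrence; clinicians who very probably know the arm may change them, and the plan describes neither masked labelling nor a record of changes.

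*Combined protocol and SAP*

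**What the plan says.** Section 6 (Outcome measures) defines the endpoint: "The primary outcome will be VT-free survival, a composite of all-cause mortality and VT recurrence one year after VT ablation". A recurrence can arise in two ways. The first is "self-terminating sustained VTs (>30 seconds or hemodynamic instability"). The second is VT that the device had to terminate, for which no minimum duration is given.

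Section 7 (ICD programming guidelines) sets detection relative to the rate of the known VT and "will allow delay in therapy of 6-12 seconds". Where the known VT is 200 bpm or faster, detection starts at 165-171 bpm, "without therapy programmed unless HR is > 200 bpm". The same section then says: "Anti-tachycardia pacing is recommended in all zones".

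On later changes, Section 7 (Follow-up) says: "Changes in medical therapy and ICD settings will be at the discretion of the treating electrophysiologist". Section 13 repeats this. ICDs are interrogated at each visit, and for patients in the arrhythmia service's VT registry "this will route us the interrogations".

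On masking, Section 5 relies on educating and reminding clinicians about the assigned group. Section 11 mentions blinding only for a later, larger trial and for the interim statistician. The plan does not say who labels device episodes as VT, whether that person knows the arm, or which device settings are extracted for analysis.

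**The concern.** For some episodes the device settings are in effect part of the endpoint definition. If settings are changed during follow-up by people who know the arm, or if episodes are labelled by people who know it, the same arrhythmia could be recorded more often in one arm than in the other. Intention-to-treat analysis does not correct this, because the problem lies in how events are found and not in who is analysed.

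Two things are at stake. The log-rank comparison could partly reflect programming or labelling instead of the drug strategy. The event rates that Section 11 wants to pass to the next trial's power calculation would carry the same error.

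**Working it through.** **Does the same episode count or not, depending on settings?** Take a stable VT lasting 15 seconds.

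- In a zone with therapy: the device may treat it after 6-12 seconds. It is then a device-terminated VT and counts.
- In a zone with detection only: it stops by itself at 15 seconds without instability, so it does not count.
- Below the detection rate: the device may not record it at all. The same holds for a longer VT.

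The 30-second gap therefore concerns stable VT of about 6-30 seconds. It does not touch deaths or VT with hemodynamic instability. The device-therapy limb might be read as excluding VT that would have stopped unaided, but once therapy is given the plan offers no way to tell these apart.

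**When can a setting change bias the primary analysis?** The log-rank test on a composite uses time to first event. A change made after a patient's first recurrence cannot alter that patient's primary outcome. Only earlier changes matter there. Later ones can still affect VT storm.

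**The plan's own figure.** The 75 per arm in Section 11 has no alpha, power, event rate or effect size behind it, so it cannot be reproduced. For scale, assuming two-sided 5% and 80% power, 75 per arm detects a fall from 40% to about 19.2%.

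**Illustration of size.** Assumptions, none from the documents: no true effect, 40% events per arm at one year, constant hazards, and extra recorded events in one arm only.

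- Apparent hazard ratio = ln(1 - p1)/ln(1 - p2), with p1 the event proportion in the arm without extra events.
- +5 points: ln(0.60)/ln(0.55) = 0.854. Expected events 75 × (0.40 + 0.45) = 63.75.
- +10 points: ln(0.60)/ln(0.50) = 0.737. Expected events 75 × (0.40 + 0.50) = 67.5.
- Chance of a significant result favouring the arm without extra events, by the Schoenfeld approximation: P(Z > 1.96 - √(D/4) × |ln HR|), with D the expected events.
- +5 points: √(63.75/4) × 0.157 = 0.63, so P(Z > 1.33) is about 9%.
- +10 points: √(67.5/4) × 0.305 = 1.25, so P(Z > 0.71) is about 24%.
- Log-rank simulation (4,000 trials) gave 2.1%, 8.4% and 23.8% for +0, +5 and +10 points.

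In patients, +10 points is 0.10 × 75 = 7.5 of the 0.60 × 75 = 45 who would otherwise be event-free, about 17%. If only 10% of those 45 were affected, recorded events would be 0.40 + 0.60 × 0.10 = 46%. The hazard ratio would be 0.83 and the two-sided rejection rate 11.7% (simulated 11.6%).

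**Direction.** It may go either way. Section 8 lists raised defibrillator thresholds as a risk of continuing the drug, which is a possible reason to reprogram the continuation arm. With the extra events in that arm, the hazard ratios for continuation invert to 1/0.854 = 1.17 and 1/0.737 = 1.36.

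**The two programming statements.** For a known VT of 200 bpm or faster, an episode between 171 and 200 bpm gets no therapy under one statement and may get pacing under the other. A stable 15-second episode there counts under the second reading only.

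**The case against.** This is a single-centre pilot in usual care, and leaving settings to the treating physician is a deliberate choice. Much of the endpoint does not hinge on settings. An obvious occasion for reprogramming is a recurrence, which is already that patient's primary event. Interrogations are available to the study, so settings may well be retrievable. All of this stands, and it limits the point.

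A reader might infer more than the documents support:

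- *That settings govern the primary endpoint as a whole.* They do not. Death is a component, and unstable VT counts before 30 seconds.
- *That the bias will occur and will favour continuation.* The documents show only that it is possible. The 5 and 10 points are assumed, and the direction is open.
- *That setting changes go unrecorded.* The plan is silent on which fields are extracted; silence is not proof.
- *That initial programming is balanced by randomisation.* Section 7 places programming after ablation but does not give its order relative to randomisation.
- *That the two programming statements contradict each other outright and add to the bias between arms.* The pacing sentence may mean all zones in which therapy is programmed. Either way the ambiguity applies equally to both arms.
- *That counting only death, shock and VT over 30 seconds would remove the dependence on settings.* It would not. Pacing after 6-12 seconds can end an episode before 30 seconds or before a shock, so the bias could reverse.

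**Conclusion.** The concern holds in a limited form. For stable VT of roughly 6-30 seconds and for VT near the detection rate, whether a recurrence is counted depends on settings that may change after randomisation. That the physicians know the arm is an inference, but a strong one, since they are reminded of the assignment and no masking of clinicians is described. No safeguard in labelling or recording is described. Ascertainment could therefore differ by arm through changes made before the first event, or through labelling.

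The size cannot be derived from the documents. Under the stated assumptions, false significance in one direction would rise from about 2% to about 8% or 24%. If fewer event-free patients were affected, the rise would be smaller. The ambiguity about pacing in all zones is a separate matter: it affects both arms alike but changes which episodes count. The point should be addressed because the remedy is cheap, and because episodes that were never detected cannot be reconstructed later.

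**What to change.** Leave physicians' freedom over settings as it is.

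1. Have existing study staff classify the routed ICD reports by study ID with the treatment arm hidden, using the Section 6 definition.
2. At each planned interrogation, record detection rate, therapy zones and delay, with the date of and reason for any change. Start with the first post-ablation setting and its date relative to randomisation. Report changes before the first event by arm.
3. Prespecify a sensitivity analysis of the primary endpoint that excludes recurrences counted only because detection was later lowered, a therapy zone added or the delay shortened. State that it is partial: episodes missed after detection is raised cannot be recovered. Do not describe shock or VT over 30 seconds as independent of pacing.
4. Reconcile the two programming statements in Section 7, so that it is clear which episodes can become device-treated recurrences. Which statement should stand is for the investigators to decide.

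The cost is a few case-report fields, one extra analysis and some time of existing staff.
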